### **Daratumumab Interruption or Missed Doses**

A daratumumab dose that is held for more than 3 days per the per-protocol administration date for any reason other than toxicities suspected to be related to daratumumab should be brought to the attention of the sponsor's Study Manager at the earliest possible time. Subjects missing  $\geq 3$  consecutive planned doses of daratumumab should be withdrawn from study treatment, unless, upon consultation with the sponsor and the review of safety and efficacy, continuation is agreed upon.

**Table 7: Infusion Rates for Daratumumab Administration**

	Dilution Volume	Initial Rate (first hour)	Rate Increment	Maximum Rate
First Infusion	1000 mL	50 mL/hour	50 mL/hour every hour	200 mL/hour
Second Infusiona	500 mL	50 mL/hour	50 mL/hour every hour	200 mL/hour
Subsequent Infusionsb	500 mL	100 mL/hour	50 mL/hour every hour	200 mL/hour

a Escalate only if there were no Grade 1 (mild) or greater infusion reactions during the first 3 hours of the first infusion.

b Escalate only if there were no Grade 1 (mild) or greater infusion reactions during a final infusion rate of  $\geq 100$  mL/hr in the first two infusions.

Infusion of daratumumab should be completed within approximately 15 hours.

### **Infusion Reactions**

Daratumumab can cause severe infusion reactions. Approximately half of all patients experienced a reaction, most during the first infusion. Infusion reactions can also occur with subsequent infusions. Nearly all reactions occurred during infusion or within 4 hours of completing DARA. Prior to the introduction of post-infusion medication in clinical trials, infusion reactions occurred up to 48 hours after infusion. Severe reactions have occurred, including bronchospasm, hypoxia, dyspnea, and hypertension. Signs and symptoms may include respiratory symptoms, such as cough, wheezing, larynx and throat tightness and irritation, laryngeal edema, pulmonary edema, nasal congestion, and allergic rhinitis. Less common symptoms were hypotension, headache, rash, urticaria, pruritus, nausea, vomiting, and chills.

Pre-medicate subjects with antihistamines, antipyretics, leukotriene receptor antagonist and corticosteroids. Frequently monitor subjects during the entire infusion. Interrupt DARA infusion for reactions of any severity and institute medical management as needed. Permanently discontinue DARA therapy for life-threatening (Grade 4) reactions. For subjects with Grade 1, 2, or 3 reactions, reduce the infusion rate when re-starting the infusion ([Table 7](#)).

### **Interference with Serological Testing:**

#### **Indirect Antiglobulin Test (IAT)**

Daratumumab interferes with the Indirect Antiglobulin Test (IAT), which is a routine pretransfusion test performed to identify a patient's antibodies to minor antigens so that suitable donor blood can be given for transfusion. Daratumumab does not interfere with ABO/RhD typing. CD38 is expressed at very low levels on erythrocytes. Daratumumab binds to the CD38 on erythrocytes, which results in a positive IAT (Indirect Coombs Test). This positive result masks the detection of antibodies to minor antigens and may prevent or delay blood banks from issuing donor blood for transfusion. This effect occurs during daratumumab treatment and for up to 6 months after treatment ends. Subjects will receive a patient identification wallet card for the study that includes the blood profile (ABO, Rh, and IAT or phenotyping) determined before the first infusion of daratumumab along with information on the IAT interference for healthcare providers/blood banks. Subjects are to carry this card throughout the treatment period and for at least 6 months after treatment ends. Blood banks can eliminate the daratumumab interference with IAT by treating reagent RBCs with dithiothreitol (DTT) ([Chapuy, 2015](#)).

Possible methods for blood banks to provide safe RBCs for transfusion to subjects receiving daratumumab include:

1. Providing ABO/RhD compatible, phenotypically (standard or extended phenotyping prior to daratumumab administration) or genotypically matched units
2. Providing ABO/RhD compatible, K-negative units after ruling out or identifying alloantibodies using DTT-treated reagent RBCs

Uncrossmatched, ABO/RhD compatible RBC units should be administered if transfusion is needed emergently as per local blood bank practice.

Despite daratumumab binding to CD38 on erythrocytes, no indication of clinically significant hemolysis has been observed in daratumumab studies ([Chari, 2017a](#)). For additional details, refer to the Daratumumab IB.

### **Overdose**

Overdose, as defined for this protocol, refers to pomalidomide, daratumumab and dexamethasone dosing only.

On a per dose basis, an overdose is defined as any amount over the protocol-specified dose of pomalidomide, daratumumab and dexamethasone assigned to a given patient, regardless of any associated adverse events or sequelae.

On a schedule or frequency basis, an overdose is defined as anything more frequent than the protocol required schedule or frequency.

Complete data about drug administration, including any overdose, regardless of whether the overdose was accidental or intentional, should be reported in the case report form. See Section [11.1](#) for the reporting of adverse events associated with overdose.

## **8.4. Method of Treatment Assignment**

This study will use the IVRS for enrollment. Designated research personnel at each investigational sites will be assigned password protected, coded identification numbers which gives them the authorization to call into IVRS to enroll Celgene approved subjects.

Celgene trial staff will review and verify specific eligibility criteria for all screened subjects prior to allowing enrollment of subjects via the IVRS. Celgene trial staff will be required to activate subjects in the IVRS before site staff may enroll the subject. For drug assignment at each cycle start and in the event of any dose reduction, site staff must contact IVRS to record the new dose level and obtain the new study treatment assignment.

## **8.5. Packaging and Labeling**

The label(s) for IP (POM, DARA, dex) will include sponsor name, address and telephone number, the protocol number, IP name, dosage form, and strength amount of IP per container, lot number, expiry date (where applicable), medication identification/kit number, dosing instructions, storage conditions, and required caution statements and/or regulatory statements as applicable. Additional information may be included on the label as applicable per local regulations.

## **8.6. Investigational Product Accountability and Disposal**

Celgene will instruct the investigator on the return, disposal, and/or destruction of investigational product (POM, DARA, dex).

## **8.7. Investigational Product Compliance**

The investigator will document the number of capsules of POM issued to and returned by each subject at each study visit. The investigator will document the number of vials of DARA administered to each subject at each DARA administration visit. For Cohort C, the investigator

will document the number of tablets of dex issued to and returned by each subject at each study visit. The investigator will also be responsible for documenting subject compliance for POM, DARA and LD-dex.

## **9. CONCOMITANT MEDICATIONS AND PROCEDURES**

### **9.1. Permitted Concomitant Medications and Procedures**

Other therapies considered necessary for the subject's well-being may be administered at the discretion of the investigator. These therapies may include antibiotics, analgesics, antihistamines, or other medications and transfusions of RBC, platelets, or fresh frozen plasma given to assist in the management of complications associated with MM or its therapy. These therapies also include pre and post infusion medications required for the administration of DARA as per Section 8.2.

The prophylactic use of hematopoietic growth factors will be allowed throughout the study at the treating physician's discretion. Once allowed, the use of myeloid growth factors is encouraged when ANC is less than 1,000/ $\mu$ L at the discretion of the treating physician.

Subjects who met the ANC, hemoglobin, and platelet eligibility criteria due to growth factor treatment or platelet/blood transfusion received prior to the start of the screening period are acceptable. Platelet and RBC transfusions are also permitted during the study.

Adjunctive radiation therapy to a pathological fracture site or to treat bone pain is permitted.

Subjects with myeloma-associated bone disease may receive bisphosphonate therapy prior to study entry, as well as other agents that may be used for myeloma-associated bone disease such as denosumab and teriparatide, unless such therapy is contraindicated. The use of bisphosphonates, as well as other agents for the treatment of myeloma-associated bone disease, is permitted throughout the study.

Thromboembolism prophylaxis: Low-dose aspirin, low molecular weight heparin, or other equivalent antithrombotic or anti-coagulant will be given to all subjects.

The following therapies will be collected and recorded in the subject's Concomitant Medication eCRF page: Anti-infectious agents, antithrombotics, growth factors, and bisphosphonates or other agents used for the treatment of myeloma-associated bone disease. All procedures, including transfusions, will be collected and recorded in the subject's eCRF.

### **9.2. Prohibited Concomitant Medications and Procedures**

Concomitant use of other approved or investigational anti-myeloma therapy within 14 days of Cycle 1 Day 1 or while the subject is taking study drug (study treatment phase) is prohibited. Subsequent anti-myeloma treatment should not be initiated prior to PD or study treatment discontinuation.

Chronic use of steroids (other than dex) or any other immunosuppressive therapies is prohibited in this study without approval from the Medical Monitor.

Drugs known to prolong the QT corrected (QTc) interval should be avoided unless deemed medically necessary. See [Appendix G](#) for a comprehensive list of drugs known to prolong QTc.

### **9.3. Required Concomitant Medications and Procedures**

Recent or active cancer is a recognized prothrombotic risk factor for increasing the risk of VTE. Increased plasma viscosity related to monoclonal paraproteinemia has been implicated as a risk

factor for VTE in MM subjects. Clinical studies have shown that thalidomide and LEN in combination with dex or other chemotherapeutic agents increase the risk of VTE ([Baz, 2005](#); [Weber, 2007](#)). Aspirin has been reported to be effective in reducing the incidence of DVT in MM subjects treated with thalidomide or LEN ([Baz, 2005](#)).

For the current study, low-dose aspirin, low molecular weight heparin, or other equivalent antithrombotic or anti-coagulant will be given during the study to all subjects. Antithrombotic prophylaxis will be recorded on the eCRF.

Pre and post infusion medications required for the administration of DARA as per Section [8.2](#) will also be recorded on the eCRF. Subjects who develop symptomatic DVT will be assessed and diagnosed objectively by Doppler ultrasonography or a comparable method. Diagnostic algorithms are provided in [Appendix A](#).

## **10. STATISTICAL ANALYSES**

### **10.1. Overview**

This is a multi-cohort study separately evaluating efficacy and safety of the combinations of POM+LD-dex (Cohort A) and POM+DARA+LD-dex combination as therapy for subjects relapsing after or refractory to LEN-based therapy in the first or second line. The primary endpoint of overall response for Cohort A will be analyzed in 2 stages; once at 6 cycles after approximately 40% of the subjects are enrolled and again after the last subject is enrolled and adequate follow up is obtained. For Cohort B and Cohort C, the primary endpoint may be assessed at timepoints allowing for early dissemination of descriptive results and after the last subject is enrolled and adequate follow up is obtained. A third analysis is planned at the end of the long-term follow-up phase of the study.

### **10.2. Study Population Definitions**

#### **Safety Population**

The safety population is defined as all enrolled subjects who receive at least one dose of the study treatment. The safety population will be used for all safety analyses.

#### **ITT Population**

The ITT population is defined as all enrolled subjects regardless of whether they received any of the study treatment. The ITT population will be used for all efficacy analyses.

#### **Efficacy Evaluable (EE) Population**

This population will consist of all enrolled subjects who meet eligibility criteria, take at least one dose of study drug, and have at least one post-baseline response assessment. The EE population will be used to provide supporting sensitivity analyses for the primary endpoint and key secondary endpoints.

### **10.3. Sample Size and Power Considerations**

The primary analysis in Cohort A will test the hypothesis that the proportion of subjects in the intent-to-treat population with ORR of 30% or greater against the null hypothesis of a response no greater than an unacceptable ORR of 16%. The 16% unacceptable ORR assumption is based on experience with carfilzomib monotherapy and the 30% ORR under the alternate hypothesis is based on a limited cohort in the Celgene CC-4047-MM-002 study. An exact binomial test with a 2-sided alpha level of 0.05 will be used to test this hypothesis. The enrollment in Cohort A was terminated at 56 subjects. Cohort A sample size will curtail the power in assessing the original hypothesis to 71%. The overall response rate can be estimated within +/- 12% with a 95% confidence interval with 55 subjects. An interim analysis will be conducted at a target of about 40% of the original planned sample size of Cohort A. There is no intent to terminate the study at interim, and the study will continue to full enrollment in order to collect an adequate amount of safety information for the POM and LD-dex combination as a third-line therapy. In order to adequately assess the primary ITT patient population analysis, the final minimum enrollment in Cohort A is 55 subjects. Accounting for drop-outs, and non-eligibility a total of approximately

65 subjects may be enrolled in Cohort A in order to support the secondary EE patient population analysis.

The primary objective for Cohort B is to estimate the overall response rate for this triplet (POM+DARA+LD-dex). A sample size of approximately 100 subjects will be adequate to estimate the overall response rate with a 95% confidence interval of width  $\pm 9.7\%$  about the obtained rate. This calculation assumes an OR rate similar to the 70% reported for this triplet combination by Chari, et al (Chari, 2015). The minimum required enrollment in Cohort B is 85 subjects. Accounting for drop-outs and non-eligibility, a total of about 100 subjects could be enrolled in Cohort B.

The primary objective for Cohort C is to test the hypothesis that the ORR for this triplet (POM+DARA+LD-dex), in Japanese participants, exceeds 25% using an exact 1-sided binomial test conducted at an alpha level of 0.025. A sample size of  $n=17$  subjects will provide 80% power for an expected ORR of 60% (Ichinohe, 2016). Accounting for the drop-outs and non-eligibility, approximately 20 subjects will be enrolled in the study. The null ORR of 25% is based on Ichinohe (2016) and the expected 60% ORR under this triplet therapy is based on Chari, et al (Chari, 2017).

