#### **10.6. Efficacy Analysis**

The primary efficacy analysis will be performed on both the ITT and EE populations. The exact binomial test will be used to test the hypothesis that the ORR for the Cohort A is greater than 16%. The final primary analysis on ORR will report exact 2-sided p-values with 95% Clopper-Pearson confidence intervals (Collett, 2003). For Cohort B point estimates of the ORR together with 95% confidence interval will be calculated using the normal approximation to the binomial distribution. Analysis for Cohort C will mirror the analysis for Cohort A except for a test of the hypothesis of an ORR greater than 25%.

The Kaplan-Meier procedures will be used to characterize the time-to-event curves (PFS, OS, TTP, and response duration) and the median and 95% confidence intervals of time to each of these events will be estimated. Univariate summary statistics will be provided for time to response. Progression-free survival and OS will be analyzed in the ITT as well as the EE populations. Other secondary efficacy endpoints will be analyzed in the ITT population only.

Analyses of PFS, OS, TTP, and response duration will be updated at the end of the long-term follow-up phase of the study.

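### Cohort A: the stated 71% power is the exact figure for 55 subjects; for the 56 enrolled it is 64% or 75%, depending on a two-sided p-value convention that the text does not name

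*Combined protocol and SAP*

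**What the plan says.** Section 10.3 sets the Cohort A primary test in the ITT population. The alternative is an ORR of 30% or more, and the "null hypothesis of a response no greater than an unacceptable ORR of 16" percent is the reference. The method is: "An exact binomial test with a 2-sided alpha level of 0.05 will be used to test this hypothesis". It then states that "The enrollment in Cohort A was terminated at 56 subjects", and directly afterwards that "Cohort A sample size will curtail the power in assessing the original hypothesis to 71" percent. The next sentence uses a different number: "The overall response rate can be estimated within +/- 12% with a 95% confidence interval with 55 subjects". Further on it says that "the final minimum enrollment in Cohort A is 55 subjects".

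Section 10.2 defines ITT as every enrolled subject, treated or not, so the denominator is 56. Section 10.6 adds the reporting rule: "The final primary analysis on ORR will report exact 2-sided p-values with 95% Clopper-Pearson confidence intervals". Neither section says how the two-sided exact p-value is formed, and neither gives the number of responders needed to reject.

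**The concern.** An exact binomial test moves in whole responders, so its power does not change smoothly with sample size. One more subject can raise the critical count by one and lower the power, or leave the count alone and raise the power. A figure worked out for 55 therefore cannot be carried over to 56 without checking.

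The null rate is not 50%, so the binomial distribution is skewed and an exact two-sided p-value can be built in more than one way. Two usual choices are to double the smaller tail, or to sum the probabilities of all outcomes no more likely than the one observed (minimum likelihood). Only doubling is guaranteed to agree with the Clopper-Pearson interval. If the plan leaves the choice open and the two differ at a plausible count, the primary conclusion for Cohort A is undefined at that count.

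**Working it through.** **Inputs.** Null ORR 0.16, alternative 0.30, two-sided alpha 0.05 and exact binomial test (Section 10.3); N = 56 enrolled (Section 10.3) and ITT = all enrolled (Section 10.2); Clopper-Pearson 95% interval (Section 10.6).

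**Formulas.** With X ~ Binomial(n, p):
- Equal-tail rule: the smallest r with P(X ≥ r | n, 0.16) ≤ 0.025. This is the same as doubled p ≤ 0.05, and the same as a Clopper-Pearson lower limit above 16%.
- Minimum-likelihood rule: the smallest r in the upper tail whose two-sided p is ≤ 0.05.
- Power: P(X ≥ r | n, 0.30). Rejections in the lower tail add less than 0.00001.

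**Reproducing the plan's figure, n = 55.**
- At 14: upper tail 0.0480, minimum-likelihood p 0.065. Neither rule rejects.
- At 15: upper tail 0.0233, doubled p 0.047, minimum-likelihood p 0.040, lower limit 16.1%. Both rules reject.
- Power = P(X ≥ 15 | 55, 0.30) = 71.7%, which is the stated 71% if the decimal is cut off.

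**The enrolled cohort, n = 56.**
- At 14: upper tail 0.0549, minimum-likelihood p 0.070. Neither rule rejects.
- At 15: upper tail 0.0272, now above 0.025, so doubled p = 2 × 0.0272 = 0.054. The minimum-likelihood p adds P(X ≤ 3) = 0.0149, giving 0.0272 + 0.0149 = 0.042. The Clopper-Pearson interval for 15/56 (26.8%) is 15.8% to 40.3%, which contains 16%.
- At 16: upper tail 0.0125, doubled p 0.025, minimum-likelihood p 0.016, lower limit 17.3%. Both rules reject.

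| Rule at n = 56 | Reject at | Upper-tail error | Power at 30% |
|---|---|---|---|
| Equal-tail (matches Clopper-Pearson) | ≥ 16 | 0.0125 | 64.1% |
| Minimum likelihood | ≥ 15 | 0.0272 (total size 0.042) | 74.5% |

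**How likely the disputed count is.** P(X = 15 | 56, 0.30) = 0.745 − 0.641 = 0.104. Under the null it is 0.0272 − 0.0125 = 0.015.

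**The precision statement.** With ORR 30%, 1.96 × √(0.3 × 0.7 / n) is 12.1% at 55 and 12.0% at 56. That sentence holds at either size; only the power figure is affected.

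**The case against.** Several points can fairly be made for the plan.

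- The 71% is correct for the stated minimum of 55, and the precision sentence beside it uses 55. The summary of changes that reduced the cohort also pairs 71% with 55 patients. That explains where the figure came from. It does not make it right where it now stands, directly after the sentence that closes the cohort at 56.
- At 56, an arcsine approximation gives 71.1% and a continuity-corrected normal approximation 71.6%. Neither is the planned exact test.
- Enrollment is closed, so a corrected power figure changes no sample size. This stands: the power error by itself alters no decision.
- Section 10.6 cites a textbook on binary data for its p-values and intervals, and Section 4.4 refers to a Statistical Analysis Plan. Either might settle the convention. The supplied text does not, and the claim goes no further than that.
- The minimum-likelihood test has total size 0.042, so it respects a two-sided 0.05. This also stands: the equal-tail rule is the better match to the required interval, but the stated alpha does not force it.

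A reader might infer that the p-value and the interval do contradict each other at 15 of 56. The documents do not support that. They conflict only if the minimum-likelihood p is used; the doubled p agrees with the interval. The conflict is possible because the convention is open, not certain.

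**Conclusion.** The stated power is wrong as written for the enrolled cohort. Under the planned exact test, 71% is the figure for 55; for 56 it is 64.1% or 74.5%, and no version of the exact two-sided test examined gives 71%. The undefined convention affects one count, 15 of 56, which has probability 10.4% at an ORR of 30% and 1.5% at 16%. At that count it determines whether Cohort A meets its primary criterion.

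The result rests on the ITT denominator being all 56 enrolled and on the convention not being fixed elsewhere. A reader might take 64% as the only correct figure; it is so only once the equal-tail rule is adopted. A reader might also infer inflated type I error from shortening the cohort after an interim look. The supplied text does not give the number of subjects in that look, and the summary of changes attributes the reduction to enrollment affected by a changed treatment landscape. No such claim is made here.

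**What to change.** In Sections 10.3 and 10.6, define the two-sided p-value as twice the one-sided exact p-value, so that it always agrees with the Clopper-Pearson interval. State that Cohort A rejects the null at 16 or more responders among the 56 ITT subjects, and replace 71% with 64% (exact, n = 56). The same rule, not the same count, should apply to the efficacy evaluable analysis if its denominator differs. This also brings Cohort A into line with the one-sided 0.025 exact test that Section 10.3 already sets for Cohort C.

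If the sponsor prefers the minimum-likelihood p-value, it should name it before the final analysis, state 15 of 56 and about 75% power, and say that at 15 responders the interval will include 16%.

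The cost is a few sentences. Under the interval-consistent rule, the stated power becomes less favourable.

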### **Study Population**

The study is anticipated to enroll approximately 188 subjects with relapsed MM or refractory MM who fulfill the eligibility criteria. At the time of this amendment, enrollment to Cohort A and B already completed with 56 and 112 subjects respectively. Cohort C will enroll approximately 20 subjects.

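### Cohort B's ±9.7% precision is stated for about 100 subjects but belongs to the 85-subject minimum; it is ±9.0% at 100 and ±8.5% at the 112 enrolled, so the error is conservative

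*Combined protocol and SAP*

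**What the plan says.** Section 10.3 makes estimation of the ORR the primary objective of Cohort B, with no null rate and no test. It ties the precision to a sample size: "A sample size of approximately 100 subjects will be adequate to estimate the overall response rate with a 95% confidence interval of width" ±9.7% around the observed rate. The planning rate follows: "This calculation assumes an OR rate similar to the 70% reported for this triplet combination".

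The same paragraph then gives two more sample-size statements: "The minimum required enrollment in Cohort B is 85 subjects", and "Accounting for drop-outs and non-eligibility, a total of about 100 subjects could be enrolled in Cohort B".

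The Study Population part of the Protocol Summary reports that "enrollment to Cohort A and B already completed with 56 and 112 subjects respectively". Sections 4.1 and 7.1 give the same counts.

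On the analysis set, Section 10.2 defines the ITT population as everyone enrolled and states that "The ITT population will be used for all efficacy analyses". Section 10.6 adds the efficacy evaluable (EE) population for the primary endpoint, which Section 10.2 describes as supporting sensitivity analysis.

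On the interval, Section 10.6 says that the Cohort B confidence interval is "calculated using the normal approximation to the binomial distribution". Cohort A gets Clopper-Pearson intervals, and the Cohort C analysis mirrors that of Cohort A.

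**The concern.** Because Cohort B is designed for estimation, the half-width is its whole sample-size justification, and the confidence interval is its primary result. A reader should be able to reproduce the stated half-width from the stated sample size, response rate and method. Here that fails.

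The paragraph is also out of date. It was revised to report that Cohort A closed at 56, but for Cohort B it still speaks of about 100 subjects who could be enrolled, although 112 have been. No precision is given for the actual sample size.

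A smaller matter is that Cohort B alone is given the normal-approximation interval, without a stated reason. Cohorts B and C receive the same triplet, so readers are likely to look at their response rates together, with intervals built in different ways.

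**Working it through.** **Inputs.** ORR 70%, two-sided 95% confidence (z = 1.96), stated half-width 9.7%, n about 100, minimum 85 (all Section 10.3); 112 enrolled (Protocol Summary, Sections 4.1 and 7.1); normal approximation (Section 10.6); all enrolled subjects in the denominator (Section 10.2).

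**Formula.** Half-width = 1.96 × √[p(1−p)/n], with p(1−p) = 0.70 × 0.30 = 0.21.

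**1. Reproducing ±9.7%.**

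| n | Source of n | Half-width at 70% |
|---|---|---|
| 85 | stated minimum | 1.96 × √(0.21/85) = 9.74% |
| 100 | n to which ±9.7% is attached | 1.96 × √(0.21/100) = 8.98% |
| 112 | actual enrolment | 1.96 × √(0.21/112) = 8.49% |

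Solving for n: 1.96² × 0.21 / 0.097² = 85.7. The stated figure therefore belongs to 85 or 86 subjects.

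**2. Could another method give 9.7% at n=100 and 70%?** Wilson gives 8.84%, the normal approximation with continuity correction 9.48%, and Clopper-Pearson an average of 9.37% (−9.98/+8.76). None does. With the plain normal approximation at n=100, 9.7% would need an ORR near 57%, not 70%.

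**3. Likely origin (an inference).** The plan gives no drop-out rate for Cohort B. If 15% was used, 85/(1−0.15) = 100 exactly. Precision was probably calculated at 85 and then attached to the inflated number. The Cohort A text in the same section supports this: it attaches ±12% to its own minimum of 55, and 1.96 × √(0.30 × 0.70/55) = 12.1%, which is correct.

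**4. Coverage of the specified interval.** Coverage at a true rate is the sum of the binomial probabilities of all outcomes whose interval contains that rate. For the normal-approximation interval at n=112:

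| True ORR | 65% | 68% | 70% | 72% | 75% | 78% | 80% | 82% | 85% |
|---|---|---|---|---|---|---|---|---|---|
| Coverage | 93.8% | 95.6% | 95.0% | 95.4% | 93.1% | 93.8% | 93.5% | 94.1% | 94.5% |

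Over ORRs of 60% to 80% the mean is about 94.5% (minimum 92.9%, maximum 95.6%), and about 82% of the rates on a fine grid fall below 95%. The mean is 94.5% over 60% to 75% and 94.2% over 75% to 85%. At n=100, coverage at 70% is also 95.0%. Clopper-Pearson at n=112 stays above 95% throughout 60% to 80%, with a mean of about 96%.

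**5. What a change of method would do.** Take 78 responders of 112 (69.6%). The normal approximation gives ±8.5 points, that is 61.1% to 78.2%. Clopper-Pearson gives 60.2% to 78.0%, that is −9.4/+8.3 points. The average half-width rises from 8.5 to about 8.9 points.

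**The case against.** The strongest reply is that nothing depends on the error. At 100 or 112 subjects the precision is better than stated, so the claim of adequacy is true, and with enrolment closed no sample-size decision remains. This stands, and it keeps the point small.

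A second reply is that ±9.7% was meant for about 85 evaluable subjects out of 100 enrolled. That probably explains the figure, but it does not rescue the text. The sentence names about 100 subjects, and the ITT population, which counts all enrolled, is the one that Section 10.2 assigns to efficacy.

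A third reply concerns the interval. Cohorts A and C test exact binomial hypotheses (null rates of 16% and 25%), to which Clopper-Pearson corresponds. Cohort B has no test, the cohorts are evaluated separately, and Clopper-Pearson has its own departure from nominal, by over-covering. The average gain of 0.4 points per side is less than half of one subject's response (1/112 = 0.9 points). This stands too, so the method change is a preference for consistency.

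Two stronger readings are tempting. A reader might infer that a wrong precision statement leaves Cohort B too small; the error runs the other way. A reader might also infer that the specified interval generally under-covers, or becomes anti-conservative above an ORR of about 75%. The calculation does not support that. Coverage at n=112 is nominal at the planning rate and moves up and down between neighbouring rates, as binomial coverage does. The average shortfall is similar on both sides of 75%.

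**Conclusion.** The precision statement is wrong as written. At the assumed 70% ORR, ±9.7% is the normal-approximation half-width for 85 subjects; it is ±9.0% at 100 (0.7 points smaller than stated) and ±8.5% at 112 (1.2 points smaller). The direction is conservative, the sample size remains adequate, and no conclusion of the trial is put at risk. The Cohort B enrolment wording in Section 10.3 is outdated against the 112 reported elsewhere.

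The choice of interval is not an error. Its average coverage deficit at n=112 is about half a point over ORRs of 60% to 80%, with dips of about two points at some rates and none at 70%. That is enough to make Clopper-Pearson a reasonable alternative, but not enough to require it.

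These figures rest on the plan's own 70% rate, on all 112 enrolled subjects being in the denominator, and on the interval method in Section 10.6. Only the account of how the figure arose is inferred.

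**What to change.** In Section 10.3, state that Cohort B enrolled 112 subjects and that, at an ORR of 70%, the 95% normal-approximation half-width is ±8.5%. If ±9.7% is kept, label it as the figure for the minimum of 85. Replace the sentence forecasting about 100 subjects with the actual enrolment. This costs wording only.

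Optionally, specify Clopper-Pearson for Cohort B in Section 10.6, in line with Cohorts A and C. If so, Section 10.3 should illustrate the precision as an asymmetric interval (78/112: 60.2% to 78.0%, or −9.4/+8.3 points) rather than as a single ± value. The cost is an interval about 0.4 points wider per side on average. If the normal approximation is kept, one sentence giving the reason would be enough.
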